## 7.2 Serious Adverse Events (SAEs)

An SAE is any AE that results in any of the following outcomes:

- Death
- A life-threatening experience
- An inpatient hospitalization or prolongation of an existing hospitalization
- A persistent or significant disability/incapacity
- A congenital anomaly/birth defect
- An event that is not listed above, but that requires intervention to prevent one of the outcomes listed above also is considered a SAE

The following will be excluded from the definition of an SAE:

- Elective hospitalizations that are not in response to an AE
- Hospitalizations that are of less than 24 hours duration
- Hospitalization related to disease progression

### 7.2.1 *Reporting of SAEs*

The recording of SAEs (regardless of their relationship to study drug) will begin with the Screening visit (signing of ICF) until the Final Visit or Early Termination Visit. Any SAE, including death due to any cause, which occurs during the conduct of this study, regardless of relationship to study drug, must be reported within 24 hours of the Investigator's (or designee's) first awareness of the event.

An initial Serious Adverse Event Form (SAE form) should be completed and submitted per the SAE form instructions.

The Investigators should attempt to group signs and symptoms into a single term that constitutes a single unifying diagnosis and indicate the serious criteria that are applicable to the SAE (the list of serious criteria is also provided in the above section). The Investigator's opinion of the relationship of the SAE to study drug, the duration, intensity, frequency, actions taken with study drug, and the outcome of the SAE will be documented using the definitions/criteria in Section 7.2.

All serious adverse events are to be reported to the Institutional Review Board (IRB) by the Investigator.

## **7.2.2 *Reporting of Suspected Unexpected Serious Adverse Reactions (SUSARs)***

SAEs that meet the criteria for a suspected unexpected serious adverse reactions (SUSARs) will be reported as an IND Safety Report to the appropriate regulatory authorities and participating investigators, in accordance with International Conference on Harmonization (ICH) guidelines and FDA regulations. A SUSAR that meets the seriousness criteria of life-threatening and/or results in death will be reported within seven (7) calendar days. A SUSAR that is not life-threatening or does not result in death will be submitted to the regulatory authorities within fifteen (15) calendar days.

Unexpected adverse reactions are adverse reactions, the nature, severity, consequences, or frequency of which are not consistent with the anticipated risks described in current relevant information (e.g., Investigator's Brochure) for the investigational product. The Investigator's Brochure serves as a primary document to provide safety reference information to determine whether an adverse reaction is expected or unexpected. Prior to submitting the appropriate IND safety report, the Sponsor will ensure that the event meets all three of the definitions for "suspected adverse reaction," "serious," and "unexpected."

## **8 EFFICACY**

Tumor assessments according to RECIST v1.1. will be performed at baseline and every 6 weeks (from C1D1) for 36 weeks, then every 12 weeks thereafter.

The Sponsor will have the option of collecting de-identified copies of all scans. The Sponsor may elect to conduct a central assessment of response prior to the completion of the study.

Other secondary efficacy endpoints (e.g., Median PFS, Best Overall Response, Time to Response, Duration of Response, Overall Survival) and tumor tissue biomarkers (in the first 10 patients) will also be assessed.

## **9 QUALITY ASSURANCE AND QUALITY CONTROL**

### **9.1 Monitoring**

Site monitoring shall be conducted to ensure that subject protection, study procedures, laboratory, study intervention administration, and data collection processes are of high quality and meet Sponsor, Good Clinical Practice (GCP)/ICH and, when appropriate, regulatory guidelines.

### **9.2 Audits and Inspections**

The Investigator will permit study-related quality audits and inspections by the Sponsor or its representative(s), government regulatory authorities, and the IRB/EC of all study-related documents (e.g., source documents, regulatory documents, data collection instruments, case report forms). The Investigator will ensure the capability for review of applicable study-related facilities. The Investigator will ensure that the auditor or inspector or any other compliance or

quality assurance reviewer is given access to all study-related documents and study-related facilities.

Participation as an Investigator in this study implies the acceptance of potential inspection by government regulatory authorities, the IRB/EC, and the Sponsor or its representative(s).

### **9.3 Safety Review Committee (SRC)**

A Safety Review Committee will govern the conduct of the study. The SRC will consist of the following individuals selected by the Sponsor:

- At least one Investigator
- The Sponsor Medical Officer or designee
- The Medical Monitor

Responsibilities of the SRC will include:

- Review of all safety data at the completion at appropriate intervals;
- Evaluation of safety data following the accrual of the initial 10 subjects (minimum 1 cycle completed); and,
- Adjusting the dose and/or schedule used in the study as appropriate based on accumulating safety data from the study.

Additional responsibilities may be asked of the SRC as appropriate to ensure subject safety.

The Safety Review Committee will meet as needed based on the rate of subject accrual (e.g., after 10 subjects (safety lead-in) and 20 subjects). SRC meetings may be conducted by teleconference or through email communications. Decisions made during the SRC meeting will be recorded in meeting minutes and will be part of the study documentation.

## **10 STATISTICAL CONSIDERATIONS**

### **10.1 General Considerations**

Data collected in this study will be presented using summary tables and subject data listings.

Continuous variables will be summarized using descriptive statistics, specifically the mean, median, standard deviation, minimum, and maximum.

Categorical variables will be summarized by frequencies and percentages.

An assessment of protocol violations, SPH4336 accountability, and other data that may impact the general conduct of the study will be presented.

The statistical and analytical plans presented below summarize the more complete plans to be detailed in the SAP. In the event of differences between the protocol and the SAP, the SAP will

prevail. The SAP will be finalized prior to database lock. Any changes to the methods described in the final SAP will be described and justified in the clinical study report.

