## 4 STUDY DESIGN

This is a multicenter, non-randomized, open-label Phase 2 study of SPH4336 in subjects with CDK4-positive liposarcomas.

SPH4336 will be administered orally once each day in successive 28-day cycles until demonstration of progressive disease or the development of unacceptable toxicity.

The study will incorporate a safety lead-in for the initial 10 subjects. Safety will be evaluated after 10 subjects (minimum 1 cycle completed) are accrued to allow a full assessment of safety by a Safety Review Committee (SRC). The study will be stopped if unacceptable toxicity is observed in more than 2 subjects based on SRC recommendation.

Tumor assessments according to RECIST v1.1. will be performed at baseline and every 6 weeks (from C1D1) for 36 weeks, then every 12 weeks thereafter. PK samples will be collected in all subjects. Baseline (pretreatment) tumor tissue will be collected from all subjects to confirm histologically a liposarcoma with a dedifferentiated component and CDK4 positivity, and in the

first 10 study subjects, tumor tissue biomarkers (phospho-Rb, Ki-67) will be analyzed in baseline (pretreatment) and C1D15 tumor tissue samples.

A Safety Review Committee (SRC) will oversee study safety and will meet at a frequency commensurate with accrual during the study (e.g., after 10 subjects (safety lead-in) and 20 subjects, and as needed).

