## **10.3 Statistical Methods**

A separate Statistical Analysis Plan (SAP) will be prepared, providing detailed methods for the analyses.

Any deviations from the planned analyses will be described and justified in the final integrated study report.

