## **5. STATISTICAL METHODS**

Descriptive statistical methods will be used to summarize the data from this study, with no hypothesis testing performed for the primary and other selected efficacy endpoints. Unless stated otherwise, the term “descriptive statistics” refers to number of subjects (N), number of observations (n), mean, median, standard deviation (SD), interquartile range, minimum, and maximum for continuous data and frequencies and percentages for categorical data.

Data required for an abbreviated clinical study report will be included in the data listings. Unless otherwise noted, the data will be sorted first by subject number, date, and time (as applicable).

The statistical analyses will be conducted with the SAS® System version 9.4 or higher.

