### **5.7.2. Primary Efficacy Analysis**

Limited efficacy analyses (tabulations) will be performed because this study ended prematurely due to futility (lack of efficacy). A by-patient listing of the objective responses evaluated by the investigators will be included in the report. The listing and table displaying duration of dosing will display the number of subjects who were dosed for 12 weeks or more without disease progression, and subjects who experienced disease progression at any time during the study, which were the criteria for inclusion in the Efficacy-Evaluable analysis dataset.

After 13 patients were enrolled in the study, too few Efficacy-Evaluable patients had reached 12 weeks of dosing without disease progression (2 of 10) to obtain a positive result for the primary study objective (see Section 3.1 Sample Size and Power). A futility analysis was performed, and it showed that the study would most likely not reach the threshold for a positive signal, even if additional patients were enrolled. A fourteenth patient was enrolled, but the study was closed (due to futility) before week 12.

Bayesian Evaluation of Futility

# Efficacy-Evaluable Patients	Stop Study if #Responses ≤
10	2
11	3
12	3
13	4
14	4
15	5
16	5
17	6
18	6
29	13

The analysis above was performed using available software (BOP2: Bayesian Optimal Phase II Design with Simple and Complex Endpoints (mdanderson.org)) and a simulation was conducted evaluating different sample sizes between current enrollment at the time of the evaluation (n=8) and full protocol enrollment (n=29).

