### **7.            CHANGES IN THE PLANNED ANALYSES**

The study ended prematurely because of a lack of efficacy in study patients. Therefore, a formal analysis of efficacy will not be performed. Biomarker analysis was also not performed.

No other changes in the planned analysis are anticipated. Should any deviations from the analyses specified in the authorized statistical analysis plan arise, such deviations will be documented in the final clinical study report.

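### Protocol 10.1 lets a SAP finalized as late as database lock override the protocol in an open-label trial; the SAP, written with 2 of 10 known, changes the analysis set and final-analysis trigger and lists neither change

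*Protocol*

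**What the plan says.** Protocol 10.1 sets the order of precedence: "In the event of differences between the protocol and the SAP, the SAP will" prevail. The only deadline it gives is "The SAP will be finalized prior to database lock". Nothing is set aside for the primary endpoint, the analysis populations, the decision rule or the timing of the final analysis.

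Two disclosure clauses go with this. Protocol 10.1 adds "Any changes to the methods described in the final SAP will be described and justified in the clinical study report", and Protocol 10.3 adds "Any deviations from the planned analyses will be described and justified in the final integrated study report".

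On visibility of outcomes, Protocol section 4 states "This is a multicenter, non-randomized, open-label Phase 2 study of SPH4336 in subjects with CDK4-positive liposarcomas". Protocol 2.2.1 makes the primary endpoint investigator-assessed, and Protocol section 8 leaves central review to the sponsor's discretion.

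The SAP is written in the past tense and already contains the result. Section 5.7.2 reports it: "After 13 patients were enrolled in the study, too few Efficacy-Evaluable patients had reached 12 weeks of dosing without disease progression (2 of 10". SAP section 5 describes the analysis as descriptive, "with no hypothesis testing performed for the primary and other selected efficacy endpoints". SAP section 7 names the missing formal efficacy analysis and the missing biomarker analysis, then closes with "No other changes in the planned analysis are anticipated".

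**The concern.** Finalizing a SAP before database lock protects against data-driven choices only if the outcomes stay hidden until then. With one arm, no masking and an investigator-read endpoint they do not: SAP 5.7.2 shows that the 12-week tally was in use while subjects were still being enrolled. A rule that lets the later document prevail then allows the denominator of the primary endpoint, and the time at which it is analyzed, to be settled with the results in view.

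The disclosure clauses do not clearly close the gap. The one in 10.1 applies to changes made after the SAP is final. The one in 10.3 refers to planned analyses, and once the SAP prevails that can be read as the SAP's own plan. A change made between protocol and SAP could therefore go unreported. What is at stake is whether a reader can tell the pre-specified 12-week count from one defined afterwards. That matters for a futility conclusion as much as for a positive one.

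**Working it through.** **1. Analysis set and trigger, side by side**

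| Element | Protocol | SAP |
|---|---|---|
| Evaluable, route 1 | 10.4.3: two or more post-baseline assessments, for the 12-week endpoint; no minimum time on treatment | 4.2: the same, with one at Week 12, plus at least 12 weeks on treatment free of progression |
| Evaluable, route 2 | 10.4.3: clinical progression | 4.2: disease progression during treatment |
| Final analysis | 10.12: accrual closed and either nobody left on study or everyone on study for at least 12 months, whichever is first | 3.4: accrual closed and nobody left on treatment, or a stop for safety or lack of efficacy |
| Listed as a change in SAP 7? | – | No, for either the set or the trigger |

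SAP 4.2 presents its version as the protocol's own definition. It is not.

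**2. Who moves between the sets**

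- A subject with two post-baseline scans who stops treatment before 12 weeks without progression is in the protocol set. The SAP set excludes this subject. Removal lowers the rate if the subject was progression-free at Week 12, and raises it if the subject progressed off treatment by then.
- A subject with a single post-baseline scan showing radiological progression, and no clinical progression recorded, is in the SAP set. Read literally, the protocol set excludes this subject. Inclusion lowers the rate.

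The rewording can therefore move the rate either way. Inclusion by SAP route 1 depends on the outcome itself, because it requires absence of progression.

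**3. The observed count**

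SAP 5.7.2 gives 13 enrolled, 10 evaluable and 2 progression-free: 2/10 = 20%, with 13 − 10 = 3 subjects uncounted. Neither document says why those 3 were not counted.

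**4. The plan's own design figures**

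Inputs, from Protocol 10.11 and repeated in SAP 3.1: p0 = 0.35, p1 = 0.60, n = 29, success at 14 or more. With X binomial(29, p):

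- Type I error = P(X ≥ 14 | 0.35) = 0.0978.
- Power = P(X ≥ 14 | 0.60) = 0.929.

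Both agree with the stated 0.1 and at least 90%. The design arithmetic is sound, and the rule is the same in both documents.

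**5. Illustration of late choice at full size**

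Assumptions, not document figures: all 33 planned subjects are dosed, 33 − 29 = 4 of them are in or out depending on the definition, and the larger set has its own properly sized cut-off of 16. At p = 0.35, P(16 or more of 33) = 0.0768. Let Y be binomial(4, 0.35) for the 4 movable subjects. Success under either set, whichever is better, occurs if X ≥ 14, or X = 13 and Y ≥ 3, or X = 12 and Y = 4.

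- P(X = 13) = P(X ≥ 13) − P(X ≥ 14) = 0.1793 − 0.0978 = 0.0815
- P(X = 12) = 0.1157
- P(Y ≥ 3) = 4 × 0.35³ × 0.65 + 0.35⁴ = 0.1115 + 0.0150 = 0.1265
- P(Y = 4) = 0.35⁴ = 0.0150
- Total = 0.0978 + 0.0815 × 0.1265 + 0.1157 × 0.0150 = 0.0978 + 0.0103 + 0.0017 = 0.1098

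The increase is 0.1098 − 0.0978 = 0.012, which takes the rate above the stated 0.10.

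**The case against.** The strongest reply is that nothing decisive was altered. SAP 3.1 repeats the 14-of-29 rule with the same null and target rates. The test was dropped because the study closed for futility with a fourteenth subject enrolled, so a 29-subject rule could no longer be applied. SAP sections 4, 5, 5.7.2, 5.7.3 and 7 all say that the efficacy analysis is curtailed. A reader might infer that the precedence clause was used to rewrite the decision rule in the sponsor's favor; the documents do not support that, and the trial made no efficacy claim.

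A reader might also infer that the rate could run from 2/13 (15%) to 5/13 (38%), either side of the SAP's futility boundary of 4 or fewer of 13. That needs all 3 uncounted subjects to be evaluable and progression-free at 12 weeks, and no passage says so. They may simply not have reached Week 12, and 10 may be the count under both definitions.

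Harsher type I figures can be produced. Holding the cut-off at 14 while removing up to 4 non-progression-free subjects from 33 gives at most P(14 or more of 33 | 0.35) = 0.236. Nothing in either document suggests exclusion by outcome on that pattern.

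Two further points stand in part. Protocol 10.3 can fairly be read as covering analyses planned in the protocol, which would make these changes reportable; even so, SAP 7 does not list them. The SAP's version history is not visible in the text, so an earlier SAP can be neither confirmed nor excluded. What is clear is that the present text was written after closure.

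**Conclusion.** The point holds as one of governance and disclosure. Protocol 10.1 allows a late SAP to override the protocol on the primary analysis set and the final-analysis trigger in a trial whose outcomes are open throughout. The SAP, written with 2 of 10 known, changes both, presents the new set as the protocol's, and lists neither change. Nothing shows that 10.1 was breached; the weakness is in what it permits.

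The size is modest. The effect on the observed rate cannot be determined without knowing why 3 of 13 subjects were uncounted. The move from 0.098 to 0.110 is an illustration that rests on the assumed 4 movable subjects and the assumed 16-of-33 cut-off. No false positive occurred.

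**What to change.** For the report now due:

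- Give the 12-week progression-free count on the Protocol 10.4.3 set first.
- Show the SAP 4.2 set beside it, labeled post hoc.
- State for each enrolled subject which set includes them and, if uncounted, why. This settles the open question about the 3 subjects.
- In SAP 4.2, remove the attribution of the definition to the protocol.
- In SAP 7, list the changes to the analysis set and to the final-analysis trigger.

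For the protocol wording, add to 10.1: *The primary endpoint, primary analysis population, decision rule and final-analysis trigger may be changed only by a protocol amendment made before 12-week outcomes are tabulated; on other methods the SAP prevails.* This comes too late to protect the present trial, but it corrects the text for reuse.

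The cost is one extra tabulation, some wording, and less freedom to refine these definitions late. The design is untouched: n = 29, cut-off 14, type I error 0.098, power 0.929.

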## **10.2 Statistical Design**

This is a multicenter, open-label, Phase 2 study of SPH4336 in subjects with advanced or metastatic liposarcoma.

## **10.3 Statistical Methods**

A separate Statistical Analysis Plan (SAP) will be prepared, providing detailed methods for the analyses.

Any deviations from the planned analyses will be described and justified in the final integrated study report.

## **10.4 Study Subjects**

### ***10.4.1 Disposition of Subjects***

The number and percentage of subjects screened and entered on study will be presented. Reasons for withdrawal will also be summarized.

### ***10.4.2 Protocol Deviations***

A summary of the number and percentage of subjects with protocol deviations by type of deviation will be provided.

### ***10.4.3 Analysis Populations***

The Safety Population will include all subjects who receive at least one dose of SPH4336.

The PK-Evaluable Population will include all subjects who have had at least one pre- and post-dose PK assessment performed.

The Efficacy-Evaluable Population will include all subjects who receive at least 1 dose of SPH4336 and meet at least one of the following 2 criteria:

- Have at least 2 post-baseline disease assessments (for PFS at 12 weeks); or,
- Experience clinical progression.

## **10.5 Demographics, Baseline Characteristics, and Concomitant Medications**

Demographic data, medical history, concomitant disease, and concomitant medications will be summarized.

Baseline characteristics will be summarized for the safety population. Subjects who died or withdrew before treatment started or do not complete the required safety observations will be described and evaluated separately.

## 10.6 Treatment Compliance

Treatment administration will be summarized including dose administration, dose modifications or delays, cumulative dose, average dose, number of doses, and the duration of therapy.

## 10.7 Efficacy Analysis

Details of efficacy analyses will be outlined in the Statistical Analysis Plan (SAP). The progression-free survival (PFS) rate and overall response rate (ORR) will be summarized with frequencies and percentages, as appropriate. The duration of response for complete and partial response subjects will be summarized with descriptive statistics (N, mean, standard deviation, median, minimum, and maximum) as well as categorically. PFS, Median PFS, Time to Response, Duration of Response and Overall Response Rate will be determined using RECIST v1.1. Kaplan-Meier methodology will be used to summarize time to events.

Subjects will be classified according to their best overall tumor response (complete response, partial response, stable disease, or progressive disease). Frequencies, proportions, and exact 95% CI of subjects, when appropriate, stratified by their best overall tumor response will be calculated. Subjects with a best overall tumor response of complete or partial with a confirmed duration of at least 4 weeks (28 days) will be further classified as having an objective tumor response. A listing of subjects with an objective tumor response will be presented.

Duration of response will be calculated as the number of days from the first documentation of response (complete or partial) to the first documentation of disease progression or death, whichever comes first.

Time to response will be calculated as the number of days from the first dose of SPH4336 to the first documentation of response.

Subjects who are alive and progression-free at the time of data analysis will be censored at the time of their last tumor assessment.

Duration of stable disease will be calculated from Cycle 1 Day 1.

Based on historical data, PFS at 12 weeks of > 60% is considered promising and a PFS of < 35% is considered not promising. A sample size of 29 subjects provides at least 90% power with type I error rate of 0.1 to decide whether the PFS rate at 12 weeks is less than or equal to 0.35 or greater than or equal to 0.60. If the number of subjects who are progression-free at 12 weeks is 14 or more, the hypothesis that the PFS rate at 12 weeks is less than or equal to 35% is rejected. If the number of subjects who are progression-free at 12 weeks is less than 14, the hypothesis that the PFS rate at 12 weeks is greater than or equal to 60% is rejected.

Tumor tissue biomarkers (phospho-Rb, Ki-67) will be analyzed by immunohistochemistry in pretreatment and C1D15 tumor tissue samples; individual and mean change from baseline in the markers and % of subjects with biomarker reductions will be determined.

The methods for all efficacy statistical analyses will be defined in the SAP.

